**Management of treatment-related anemias is provided in [Table 4](#).**

**Table 3:** Evaluation Guidance of Suspected Treatment-related Anemia AEs

Basic anemia evaluation (prior to transfusion, if feasible)	
CBC with differential (e.g. MCV, RDW, ANC, hemoglobin, hematocrit) Reticulocytes counts Peripheral blood smear for cell morphological assessment Complete metabolic panel including liver panel-LFTs, bilirubin, LDH, renal function, and serum folate, B12 values and other chemistries Coagulation factors (PT, PTT, INR) Urinalysis including culture Iron panel (TIBC, ferritin, Fe) TSH/thyroid panel Fecal-occult blood testing Erythropoietin Haptoglobin	
Further recommendation based on suspected etiology (in addition to baseline anemia testing)	
Unknown etiology, suspect possible hemolysis	Coombs test, fibrinogen, d-dimer Consider hematology consultation. Consider blood transfusion at clinical discretion.
Unknown etiology, suspect possible bleeding	Consider blood transfusion at clinical discretion. Consider surgical/interventional radiology consultation. Consider imaging, as clinically indicated (e.g. FAST scan, CT scan, MRI, angiography). Consider endoscopy (upper/lower)
Unknown etiology despite above work-up	Hematology consultation Consider bone marrow aspiration/morphologic evaluation

**Table 4: Management of Treatment-Related Anemia**

 
• Hematology assessment must be performed at baseline, prior to each bintrafusp alfa dose, at the end of treatment visit and at 28 (<math>\pm 5</math> days) days post-treatment safety follow-up.
 
• Participants must enter the study with Hgb values at least 9g/dl
 
• All relevant hematological testing for treatment-related anemias should be done prior to a blood transfusion, if clinically feasible
 

Diagnostic Work-up

 
• Baseline Anemia Evaluation               
 
• CBC with emphasis on red cell indices
 
 
 
• If indicated and at clinical discretion, the following should be considered:               
 
• Iron studies
 
• Serum Folate and Vit B12 values
 
• Coagulation factors
 
• Fecal occult blood
 
• Urinalysis
 
• Hormone panel: TSH, Erythropoietin
 
• Peripheral blood smear
 
 
 

Further recommendation based on suspected etiology (in addition to basic anemia testing)

 
• Suspected Hemolysis 
 
• bilirubin, LDH, Coombs test, haptoglobin
 
 
 
• Suspected bleeding: 
 
• Consider imaging/interventional radiology consultation as indicated
 
• Consider imaging and/or endoscopy as clinically indicated
 
 
 
• Suspected aplastic anemia: 
 
• Hematology consultation
 
• Consider bone marrow aspiration/morphologic evaluation
 
 
 

Additional consideration
In general, blood transfusions and erythroid growth factors are permitted as clinically indicated.

### 3.3.1.10 Rash with Hyperkeratosis / Keratoacanthoma / Squamous Cell Carcinoma of the Skin

Monitoring will include skin assessments every 4 weeks with biopsy of suspicious lesions. Dermatological consults should be requested as needed. Treatment modifications for reactions caused by M7824 are addressed in [Table 5](#).

**Table 5:** Management of M7824 mediated Skin Reactions

 
• Hyperkeratosis
 
• Keratoacanthoma
 
• Cutaneous squamous cell carcinoma (cSCC)
 
• Basal cell carcinoma
 
• Actinic keratosis
 

Management

 
• Discontinuation or termination not required in most cases. Continuation of treatment should be evaluated by the Investigator.
 
• Emollients may be used
 
• Develop diagnostic and treatment plan in collaboration with Investigator and dermatologist
 
• Treatment follow-up will depend on number and localization of lesions. 
 
○ Single lesion: full excision may be recommended
 
○ Multiple lesion or location not suitable for full excision: Mohrs surgery, cryotherapy or other standard treatment options depending on pathology. Retinoids may be used per Investigator decision.
 
 
 
• Close clinical follow-up for re-evaluation, resolution and potential recurrence should be implemented
 
• In general, treatment of M7824 mediated skin lesions should be based on local guidelines/standard of care.
 

Additional consideration: Keratoacanthoma lesions may resolve spontaneously without surgical intervention within weeks after discontinuing bintrafusp alfa.
 
Consult with Medical Monitor as needed for management of M7824 mediated skin lesions.

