#### 3.3.1.2 Adverse Drug Reactions (ADRs) Requiring Treatment Discontinuation

**Any Grade 4 ADRs require permanent treatment discontinuation** except for single laboratory values out of normal range that do not have any clinical correlate, and resolve to Grade  $\leq 1$  or baseline grade within 7 days with adequate medical management. Grade 3 or 4 symptomatic endocrinopathies (e.g., thyroiditis or hypophysitis), treatment should be delayed and treatment started according to NCCN guidelines. If condition improves to Grade 1, treatment may be resumed.

Subjects with grade 4 amylase or lipase abnormalities must permanently discontinue treatment. If the participant develops any evidence of pancreatitis, it should be managed accordingly.

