**Any Grade 3 ADRs require treatment discontinuation except for any of the following:**

- Transient ( $\leq 6$  hours) Grade 3 flu-like symptoms or fever, which is controlled with medical management.
- Transient ( $\leq 24$  hours) Grade 3 fatigue, local reactions, headache, nausea, emesis that resolves to  $\leq$  Grade 1 or Baseline grade.
- Tumor flare phenomenon defined as local pain, irritation, or rash localized at sites of known or suspected tumor that resolves within 7 days with optimal medical management.
- Any single Grade  $\geq 3$  drug-related transaminase, alkaline phosphatase, or bilirubin abnormality with no other associated laboratory (or other) abnormality that is not associated with symptoms or clinical manifestations of hepatitis. If the liver function abnormality not associated with symptoms or clinical manifestations of hepatitis has not resolved to Grade  $\leq 1$  within the subsequent 2 cycles (28 days), the subject should permanently discontinue treatment with M7824.
- Subjects with asymptomatic Grade 3 drug-related amylase or lipase abnormalities may continue treatment.
- .
- Grade 3 Hgb decrease ( $< 8.0$  g/dL) that is clinically manageable with blood transfusions or erythroid growth factor use.
- Increases in Eastern Cooperative Oncology Group performance status (ECOG PS)  $\geq 3$  that resolves to  $\leq 2$  by Day 1 of the next cycle (infusions should not be given if the ECOG PS is  $\geq 3$  on the day of M7824 administration and should be delayed until ECOG PS  $\leq 2$ ).
- Keratoacanthoma and squamous cell carcinoma of the skin. Any suspicious skin lesion should be biopsied for confirmation of diagnosis and be surgically removed as indicated by dermatologist and a dermatological consult obtained.
- Other immune-related ADRs, see NCCN guidelines for the management of immune related adverse events

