### 8.1.6 Adverse Events of Special Interest (AESI)

Adverse events of special interest (AESIs) are serious or nonserious AEs that are of clinical interest and should be closely followed.

AESIs include following:

- Infusion-related reactions including immediate hypersensitivity.
- Immune-related adverse events.
- M7824 mediated skin reactions.
- Anemia.
- Bleeding AEs

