IRR is a composite term which includes Reactions: Anaphylactic reaction, Drug hypersensitivity, Hypersensitivity, Infusion related reaction, Type I hypersensitivity and Signs and Symptoms: Abdominal pain, Back pain, Chills, Dyspnoea, Flushing, Hypotension, Pyrexia, Urticaria, Wheezing.

irAEs identified risk for M7824 (based on PDL-1blockade) are Thyroiditis, autoimmune thyroiditis, hypothyroidism, hyperthyroidism, Diabetes mellitus, Type I diabetes, type I diabetes mellitus, adrenal insufficiency, adrenalitis, Colitis Enteritis, enterocolitis, Nephritis, acute kidney injury, Myositis, Retinal microvasculitis, retinal vasculitis, rash, rash generalized, maculo-papular rash, erythematous, rash, pruritic rash, pemphigoid, Pneumonitis Interstitial pneumonitis, Interstitial lung disease.

irAEs potential risks for M7824 are Guillain-Barré syndrome, uveitis, pancreatitis, myasthenia gravis/myasthenic syndrome.

Skin AE ( TGF- $\beta$  blockade mediated) include rash with hyperkeratosis, cutaneous squamous cell carcinoma, keratoacanthoma.

*Abbreviated Title: Phase II M7824 in UC*

*Version Date: 06/23/2021*

Important potential risks includes treatment related anemia, delay in wound healing and embryofetal toxicity.

As of October 2018, more than 670 patients have been treated with M7824 1200mg flat dose q2w across multiple solid tumor expansion cohorts.

The safety profile is consistent with other monotherapy checkpoint inhibitors, with the exception of keratoacanthomas and cutaneous squamous cell carcinomas ( similar to anti-TGF- $\beta$  targeting therapy Fresolimumab and TGF- $\beta$  genetic mutation inheritance -Ferguson- Smith Syndrome) which have occurred in approximately 7% of M7824 treated patients, and are well managed with surgical excision. These lesions have not been a criterion for treatment discontinuation.

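### Section 3.3.1.2 and Table 5 conflict on a drug-related Grade 3 hyperkeratosis, basal cell carcinoma or actinic keratosis: one requires stopping M7824, the other leaves it to the investigator

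*Combined protocol and SAP*

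**What the plan says.** Two parts of the protocol govern whether M7824 continues after a drug-caused skin lesion.

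- **Section 3.3.1.2** works by grade. Its Grade 3 rule reads "Any Grade 3 ADRs require treatment discontinuation except for any of the following". The one exception that names skin lesions opens with "Keratoacanthoma and squamous cell carcinoma of the skin" and goes on to work-up: "Any suspicious skin lesion should be biopsied for confirmation of diagnosis and be surgically removed as indicated by dermatologist". The last exception is for other immune-related reactions, which are referred to the NCCN guidelines.
- **Section 3.3.1.10** works by lesion type. It states that treatment modifications for reactions caused by M7824 are in Table 5. The table lists hyperkeratosis, keratoacanthoma, cutaneous squamous cell carcinoma, basal cell carcinoma and actinic keratosis. For all five it says "Discontinuation or termination not required in most cases. Continuation of treatment should be evaluated by the Investigator". It gives no grade.

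Section 8.1.6 lists "M7824 mediated skin reactions" as an adverse event of special interest, in a separate bullet from immune-related adverse events.

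**The concern.** An investigator facing a drug-related Grade 3 event of one of the three lesion types that Table 5 lists and Section 3.3.1.2 does not exempt can find two instructions. An investigator who turns to Table 5, as Section 3.3.1.10 directs, may judge that treatment can continue. One who turns to Section 3.3.1.2 finds that discontinuation is required. Two patients with the same event could be handled differently. Continuing under Table 5 could also be recorded as protocol non-adherence, which Section 8.8 defines as any noncompliance with the protocol. At stake are consistent decisions about who stays on drug and, through them, exposure and the reasons recorded for stopping. Safety is a secondary objective (Section 1.1.2).

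**Working it through.** No formula applies, and the plan gives no figure to reproduce. The check sets the two texts side by side and then looks for a clause that reconciles them.

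**Step 1: scope.** Table 5 is introduced as covering reactions caused by M7824, so its events are drug reactions and fall within the subject of Section 3.3.1.2. Grade 3 and 4 events unrelated to the drug are handled in Section 3.3.1.12 and are outside this point.

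**Step 2: lists at Grade 3.**

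| Lesion in Table 5 | Named in the Grade 3 exceptions of 3.3.1.2 | 3.3.1.2 at Grade 3 | Table 5 |
|---|---|---|---|
| Keratoacanthoma | Yes | Exempt | Investigator evaluates |
| Cutaneous squamous cell carcinoma | Yes | Exempt | Investigator evaluates |
| Hyperkeratosis | No | Stop required | Investigator evaluates |
| Basal cell carcinoma | No | Stop required | Investigator evaluates |
| Actinic keratosis | No | Stop required | Investigator evaluates |

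The count is 5 listed − 2 exempt = 3 unmatched.

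**Step 3: is there a reconciling clause?**

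1. *The biopsy sentence in the skin exception.* It covers any suspicious lesion, but it directs biopsy and removal. It adds no lesion to those exempt from discontinuation.
2. *The exception for other immune-related reactions.* It does not clearly apply. Section 8.1.6 keeps the M7824 skin reactions apart from immune-related events. Section 14.1.2 points the same way for one of the three, since its skin reactions attributed to TGF-β are described as "blockade mediated) include rash with hyperkeratosis, cutaneous squamous cell carcinoma, keratoacanthoma". That text does not mention basal cell carcinoma or actinic keratosis, so for those two the support is Section 8.1.6 alone.
3. *The remark in Section 14.1.2 that these lesions have not been a criterion for stopping.* It refers to keratoacanthomas and cutaneous squamous cell carcinomas, the two lesions already exempt.
4. *A precedence statement.* Neither Section 3.3.1.2 nor Section 3.3.1.10 refers to the other or says which prevails.

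None of the four closes the gap for the three unmatched lesions.

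**The case against.** The strongest reply is that Table 5 is hedged. It says only that stopping is usually unnecessary, so a Grade 3 event can be one of the remaining cases. On that reading a site that stops under Section 3.3.1.2 breaches nothing in Table 5. This stands in part: the two rules can both be satisfied by stopping. The conflict runs the other way, because a site that uses the discretion in Table 5 and continues may breach Section 3.3.1.2. Table 5 does not say that Grade 3 lies outside its discretion. Table 6, on bleeding, shows that the protocol sets dosing instructions by grade when it means to.

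A second reply is that the specific table overrides the general rule. The documents do not say so. If it did, the exception for keratoacanthoma and squamous cell carcinoma in Section 3.3.1.2 would be unnecessary. If instead Section 3.3.1.2 overrides the table, the discretion in Table 5 is empty at Grade 3 for three of its five lesions. Each reading leaves some text without effect.

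A third reply is that Table 5 offers consultation with the Medical Monitor. That is a practical route for a single case, but it does not settle which rule the consultation should apply.

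It is also fair that Section 3.3.1.2 calls Grade 3 discontinuation required without calling it permanent, whereas for Grade 4 it does. The Grade 3 requirement may thus be less final than it first reads, but it is still a requirement set against a discretion.

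**Conclusion.** The text is wrong as written, and the point is minor. For drug-related Grade 3 hyperkeratosis, basal cell carcinoma and actinic keratosis, one section requires discontinuation and the other leaves it to the investigator, with no stated precedence. The size is three of the five lesion types in Table 5. The number of patients affected cannot be derived: the documents give no Grade 3 rate for these three lesions, and it could be zero. The definition of ORR, the Simon rules, the 68 evaluable patients and the ceiling of 75 are unaffected. The conclusion assumes that the event is judged related to M7824 and is not classed as immune-related.

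A reader might infer three stronger points that the documents do not support.

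- *A separate conflict at Grade 4.* Section 3.3.1.2 says "Any Grade 4 ADRs require permanent treatment discontinuation", and its exceptions do not concern skin lesions. Table 5 makes no Grade 4 statement. A hedged, ungraded table does not contradict an explicit mandate for that grade.
- *Competing definitions of the skin event of special interest.* The term in Section 8.1.6 matches the title of Table 5, the list in Section 14.1.2 is not worded as exhaustive, and the list in Section 3.3.1.2 is a dosing exception. Section 10 plans no tabulation of these events that would change.
- *A frequency of about 7%.* Section 14.1.2 gives that figure for keratoacanthoma and cutaneous squamous cell carcinoma, which are not in dispute at Grade 3. It says nothing about the other three.

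**What to change.** Reconcile the two passages:

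1. Make the Grade 3 exception in Section 3.3.1.2 and the lesion list in Table 5 agree, so that each of the five lesion types has one instruction at Grade 3.
2. Add to Table 5 a cross-reference stating how it relates to the grade-based rules in Section 3.3.1.2.

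The sponsor's clinicians decide what the rule should be; this review takes no view on it. The cost is a wording amendment to Section 3.3.1.2 and Table 5, with the IRB approval that the protocol requires for any amendment. It adds no patients, visits or procedures and changes no analysis.

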### 3.3.1.11 Impaired Wound Healing o

Management should be discussed on a case-by-case basis. Dermatological consults should be requested as needed.

- Impaired wound healing is considered an important potential risk for bintrafusp alfa
- Management should be discussed with Medical Monitor for participants requiring surgery on study.
- It is recommended to hold study intervention for approximately 4 weeks post major surgery for observation.
- Post-operative wound healing should be closely monitored

### 3.3.1.12 Dose Interruptions for Adverse Events not Related to Study Drug

In case of Grade 3 and Grade 4 AEs not study drug related, the study treatment may be interrupted based on the investigator assessment and the subject will be medically treated for the event.

If the AE reduces to a lower tolerable grade the study treatment might be resumed in the subsequent cycle. If the AE remains the same despite the medical treatment until the next treatment (second cycle after the AE occurred) a consideration of a possible extension of the dose interruption for up to 1 additional cycle or a permanent withdrawal from the study treatment should be considered.

If upon the resumed study treatment, the subject experiences the same AE, permanent withdrawal from the study treatment should be considered.

Grade 3 and 4 laboratory abnormalities that do not have clinical significance and are not related to study drugs do not require dose interruption.

### 3.3.1.13 Embryo-Fetal Toxicities

Embryo-fetal toxicities are a known risk of the PD-1/PD-L1 targeting class and are considered important potential risk for M7824. Animal models link the PD-1/PD-L1 signaling pathway with maintenance of pregnancy through induction of maternal immune tolerance to fetal tissue [34-37]. Embryofetal toxicity is an important potential risk of bintrafusp alfa. Embryo-fetal and reproductive toxicities have also been investigated in animal models for a humanized mAb targeting TGF $\beta$ 1. At doses as high as 30 mg/kg, no maternal reproductive toxicity or embryo-fetal lethality were observed in rabbits [38]. To mitigate these potential risks, pregnant participants are excluded from the study, and all participants of childbearing/conceiving potential must use highly effective contraception (See Section 2.1.1.11).

### 3.3.1.14 Mild to Moderate Bleeding Events

Bleeding events of mild to moderate severity were observed in participants treated with M7824 in ongoing studies and are a potential risk for M7824. Events may include epistaxis, hemoptysis, gingival bleeding, or hematuria among others. In general, majority of these events were observed to be self-limiting, did not require intervention, and resolved without discontinuation of study treatment.

Management of bleeding is provided in **Table 6**.

**Table 6: Management of Bleeding Adverse Events**

Bleeding Adverse Events	

 
• Bleeding adverse events are considered important identified risk for bintrafusp alfa.
 
• In general, mild and moderate mucosal bleedings resolve without discontinuation of treatment.
 
• These events may include, but are not limited to the following:               
 
○ Epistaxis
 
○ Hemoptysis
 
○ Gingival bleeding
 
○ Hematuria
 
 
 
	
Non-tumor Bleeding	
Grading	Management
Grade 2	
 
• If resolves to Grade <math>\leq 1</math> by the day before the next infusion, study intervention may be continued
 
• If not resolved to Grade <math>\leq 1</math> by the day before the next infusion, but is manageable and /or not clinically relevant, consult Medical Monitor to assess if clinically reasonable to administer the following infusion.
 

Grade 3	
 
• Permanently discontinue treatment unless an alternative explanation can be identified (such as concomitant use of antithrombotic agents, traumatic events, etc.)
 
• In case of alternative explanations, hold study treatment until the event recovers to Grade <math>\leq 1</math>
 

Grade 4	
 
• Treatment must be permanently discontinued if no alternative explanation is identified.
 

Tumor Bleeding	
Grade $\geq 2$	
 
• Study treatment must be held till the event recovers to Grade <math>\leq 1</math>
 
• Permanently discontinue treatment if the Investigator considers the participant to be at risk for additional severe bleeding.
 

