## 3.3 DOSE MODIFICATIONS

### 3.3.1 M7824

M7824 is planned to be administered at 1200 mg (flat dose) every two weeks. Dosing may be delayed up to 12 weeks for toxicity or logistical reasons, including the inability of the patient to get to the clinic. Dose reductions are not allowed.

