### 8.1.5 Relationship to Study Product

All AEs will have their relationship to study product assessed using the terms: related or not related.

- Related – There is a reasonable possibility that the study product caused the adverse event. Reasonable possibility means that there is evidence to suggest a causal relationship between the study product and the adverse event.
- Not Related – There is not a reasonable possibility that the administration of the study product caused the event.

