## **12 HUMAN SUBJECTS PROTECTIONS**

### **12.1 RATIONALE FOR SUBJECT SELECTION**

Cisplatin ineligible or platinum refractory metastatic urothelial cancer patients may have received prior checkpoint inhibitor therapy or be checkpoint inhibitor naïve to enroll. Patients with metastatic urothelial cancer who received prior checkpoint inhibitors are left with limited options and the effect of subsequent immunotherapy treatment is unknown. While current PD-1/PD-L1 checkpoint inhibitors have shown efficacy in checkpoint naïve patients who are either cisplatin ineligible or refractory response rates are about 20% [46]. Therefore, it is imperative to improve on this response rate with drugs like M7824 that have potential of increasing response rates through immunomodulation. These reasons express the need to determine M7824 activity in our patient population.

Participants who do not accept blood transfusions will be excluded. As there is a risk of severe bleeding with this study drug, participants must be willing to receive blood transfusions if medically necessary for their own safety. Participants must be able to receive blood transfusions in order to minimize the risks of receiving M7824. Another reason for this is that including these patients could compromise the scientific validity of the study. For example, death from blood loss could make it difficult to assess other aspects of the investigational immunotherapy's safety—a primary scientific goal in this early-phase immunotherapy trial, which are carried out in small numbers of participants.

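### Table 6 leaves permanent stopping after a drug-related Grade 4 tumor bleed to investigator judgement, where 3.3.1.2 makes it mandatory, and it states no hold for a Grade 4 non-tumor bleed that has another explanation

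*Combined protocol and SAP*

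**What the plan says.** The general stopping rule is in protocol section 3.3.1.2. At Grade 4: "Any Grade 4 ADRs require permanent treatment discontinuation". The relief given there is for isolated laboratory values without a clinical correlate that resolve within 7 days, and symptomatic endocrinopathies are handled separately. At Grade 3: "Any Grade 3 ADRs require treatment discontinuation except for any of the following". The list that follows includes tumor flare, manageable hemoglobin decreases, skin lesions and other immune-related reactions. It does not include bleeding.

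Bleeding has its own section, 3.3.1.14, which says "Management of bleeding is provided in" Table 6. The table separates non-tumor from tumor bleeding. The tumor part is a single row for Grade 2 and above with two instructions: "Study treatment must be held till the event recovers to Grade" 1 or less, and "Permanently discontinue treatment if the Investigator considers the participant to be at risk for additional severe bleeding". The row is not divided by grade or by relatedness.

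For non-tumor bleeding, Grade 3 means a permanent stop unless another explanation is found, in which case treatment is held to Grade 1 or less. Grade 4 means a permanent stop if no other explanation is found. The table does not say what to do at Grade 4 when there is one.

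**The concern.** An investigator with a bleeding patient is sent to Table 6. For a Grade 4 tumor bleed judged related to the drug, that table asks for a hold and a judgement, while 3.3.1.2 has already decided that treatment ends. Nothing in Table 6 refers back to 3.3.1.2.

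What is at stake is re-exposure after a life-threatening event. Section 12.1 justifies an eligibility restriction with the words "As there is a risk of severe bleeding with this study drug", and Table 6 itself treats bleeding as an identified risk of the drug. Section 3.3.1 allows dosing to be delayed for up to 12 weeks, and "Dose reductions are not allowed", so any resumption would be at the full 1200 mg.

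The table is also uneven within itself. An unexplained Grade 3 non-tumor bleed ends treatment, but a Grade 4 tumor bleed need not. In the non-tumor part, the more severe grade has the less complete instruction.

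**Working it through.** The plan gives no figure to reproduce here. The check compares the rules for the same event.

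**Can a tumor bleed be an adverse drug reaction under this protocol?** Yes. Section 8.1.5 classes each event as related or not related, and related requires only this: "There is a reasonable possibility that the study product caused the adverse event". Related tumor bleeds are therefore a subset of the Table 6 row.

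**Tumor bleed judged related, by grade:**

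| Grade | General rules | Table 6, tumor row | Difference |
|---|---|---|---|
| 2 | 3.3.1.3: treatment may continue under conditions | Hold to Grade 1 or less; permanent stop on judgement | Table 6 is stricter; 3.3.1.2 does not apply |
| 3 | 3.3.1.2: discontinue, not described as permanent | Same row | Partial |
| 4 | 3.3.1.2: discontinue permanently | Same row | Clear: mandatory against judgement |

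**Does an exception in 3.3.1.2 remove the difference?** No. Tumor flare is defined there by pain, irritation or rash. The hemoglobin item concerns a laboratory decrease, not the bleed that caused it. Skin lesions and immune-related reactions are listed; bleeding is not.

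**Does another clause decide which rule governs?**
- Section 3.3.1.14 points to Table 6 without mentioning 3.3.1.2, and its title refers to mild to moderate events.
- The precedence wording in 3.3.1.8 is confined to immune-related events.
- Section 3.3.1.12 covers Grade 3 and 4 events that are not drug-related.
- The removal criteria in 3.6.1 do not address the point.

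**Non-tumor bleed with an alternative explanation:**
- Grade 3: Table 6 mandates a hold to Grade 1 or less.
- Grade 4: Table 6 states no action. If the event is nevertheless judged related, 3.3.1.2 still ends treatment when the two rules are applied together. If it is judged unrelated, only 3.3.1.12 remains, and there interruption is optional.

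**How many patients?** The table in section 14.1.2 lists tumour haemorrhage in 10 of 630 patients (10/630 = 1.6%). Applied to the accrual ceiling of 75, that is 75 × 10/630 = 1.2 patients. This does not measure the disputed subset. The table gives no grades. Its caption describes treatment-related events leading to discontinuation, but rows such as any serious adverse event (58.9%) and disease progression (7.8%) suggest all-cause serious events. The share that is both related and Grade 3-4 cannot be recovered from it.

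**The case against.** The strongest reply is that both texts can be obeyed together. Section 3.3.1.2 is categorical at Grade 4, and nothing tells a site to disregard it. The tumor row adds duties (a hold, and a stop when further severe bleeding is feared) and never expressly permits resumption, whereas the non-tumor Grade 2 row does. Holding until recovery implies that some patients resume, but the row also covers Grade 2 and unrelated bleeds, for which resumption is consistent with the other rules. This stands. A reader might infer that the protocol contradicts itself outright, or that Table 6 overrides 3.3.1.2; the documents support neither. What remains is that the cumulative reading is nowhere written, and the section on bleeding directs the investigator to the table alone.

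A second reply is that the tumor/non-tumor split may stand in for cause, since section 14.1.2 distinguishes bleeding due directly to the cancer from a possible drug effect. For unrelated tumor bleeds this helps the plan, because Table 6 is then stricter than the optional interruption of 3.3.1.12. It does not cover the related bleed, which 8.1.5 allows and the row does not exclude.

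Third, the Grade 3 argument is weak without the word permanent. That is accepted: at Grade 3 the intended outcome is for the sponsor to state.

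Finally, weekly patient review (7.4.1), special-interest status for bleeding (8.1.6) and 24-hour reporting of serious events (8.3) make unnoticed re-dosing less likely. They do not say which rule applies.

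**Conclusion.** The point holds in a narrow form, and it is minor. For a Grade 4 tumor bleed judged related to M7824, Table 6 read alone permits full-dose re-treatment that 3.3.1.2 rules out. In practice this matters only where the investigator sees no further risk of severe bleeding, since otherwise both rules stop treatment. At Grade 3 there is a softer divergence. The missing hold for an explained Grade 4 non-tumor bleed is a separate omission, of consequence when the event is judged unrelated.

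The conclusion rests on the wording of the sections compared and on the possibility, under 8.1.5, that a tumor bleed is classed as related. A reader might take the 10 of 630 as the number of patients exposed to the ambiguity; for the reasons given above it is not, and no frequency is claimed. Nor should one infer an effect on the efficacy conclusions: the two-stage response rules, their error rates and the sample sizes are unaffected.

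**What to change.** Amend two rows of Table 6.

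- Tumor bleeding, Grade 2 and above: keep the present hold and judgement, and add that a Grade 4 bleed judged related means permanent discontinuation under 3.3.1.2, and that 3.3.1.2 also applies to a Grade 3 bleed judged related.
- Non-tumor bleeding, Grade 4: add that, where an alternative explanation is identified, treatment is held until Grade 1 or less, as at Grade 3.

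This follows the sponsor's own general rule. If the sponsor instead wants investigator discretion after related Grade 3-4 tumor bleeds, listing that exception in 3.3.1.2 would also leave one rule, but it should then be a stated choice.

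The cost is a wording change in a protocol amendment, with no added patients, visits or procedures. The downside is that a rare patient with a related Grade 3-4 tumor bleed loses the chance of re-treatment.
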